12.1.2.1. Hypotheses

Statistical testing will be performed to determine if the de novo dyspareunia rate of treatment group is non-inferior to the control group. The null hypothesis is that the de novo dyspareunia rate in treatment group is greater than or equal to the rate in control group plus margin:

$$H_0: \pi_{treatment} - \pi_{control} \geq \Delta$$

The alternative hypothesis is:

$$H_a: \pi_{treatment} - \pi_{control} < \Delta$$

where $\pi_{treatment}$ and $\pi_{control}$ are the de novo dyspareunia rate in treatment group and control group respectively, and $\Delta > 0$ is defined as the non-inferiority margin.

Statistical testing will be performed to determine if the AE incidences (pelvic pain, infection, vaginal shortening, atypical vaginal discharge, neuromuscular problems, vaginal scarring, de novo vaginal bleeding, fistula formation and/or de novo voiding dysfunction) rate of treatment group is non-inferior to the control group. The null hypothesis is that the AE incidences rate in treatment group is greater than or equal to the rate in control group plus margin:

$$H_0: \pi_{treatment} - \pi_{control} \geq \Delta$$

The alternative hypothesis is:

$$H_a: \pi_{treatment} - \pi_{control} < \Delta$$

where $\pi_{treatment}$ and $\pi_{control}$ are the AE incidence rates in treatment group and control group respectively, and $\Delta > 0$ is defined as the non-inferiority margin.

The propensity score adjusted confidence intervals described in Section 12.2.3. (Propensity Score Methodology) will be used to summarize the mean score improvement of Quality of Life (PFIQ, PFDI, PISQ, TOMUS pain scale) of the mesh (treatment) group compared to that of the native repair (control) group.

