12.1.2.3. Statistical Methods

A comparison of data for all subjects will be included per the following statistical analyses to measure for secondary endpoints:

- Rate of adverse device or procedural-related effects within 6, 12, 18, 24 and 36 months
- Overall rate of adverse device or procedural-related effects within 6, 12, 18, 24, 36 months
- Comparison of adverse device or procedural-related effects between treatment groups
- Rate and severity of mesh exposure and erosion within 6, 12, 18, 24, 36 months
- Assessment of rate of adverse device or procedural-related effects in subjects with reoperation for failed prolapse repair
- Assessment of rates of/times to reoperation
- Comparison of rate of adverse device or procedural-related events in subjects with re-surgery in both treatment groups
- Assessment and comparison between groups of analgesic intake and pain scoring at post-operative 6 weeks, 12, 18, 24, 36 months. Pain score improvement will be analyzed with a paired t-test for each group on all patients and with the propensity score adjusted confidence intervals for the pain score differences between groups. Change in analgesic intake from baseline will be analyzed by McNemar's test for each group on all patients.
- Assessment of severe blood loss during surgical procedure
- Duration of surgery from operative report
- Assessment of re-treatment interventions (i.e. surgery, office-procedure, etc.)
- Assessment of days to discharge and return to normal activity
- Assessment of risk factors, including menopausal status, estrogen use, age smoking, diagnosis of diabetes, body mass index, concomitant procedures, surgeon training and experience

A comparison of data between baseline and 36 months for all subjects will be included per the following statistical analyses to measure for secondary endpoints:

- Quality of Life Assessments (PFIQ, PFDI, PISQ, TOMUS) at 6, 12, 18, 24, 36 months as compared to baseline: paired t-test will be used to compare mean QOL score improvement from baseline to 6, 12, 18, 24 and 36 months for each group.
- Comparison of Quality of Life Assessments improvements between treatment groups
- Assessment of Quality of Life in subjects with re-surgery after re-surgery
- Assessment of subject satisfaction at 6, 12, 18, 24, 36 months (PGI-I for Prolapse)

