Propensity score adjusted confidence intervals described in Section 12.2.3 (Propensity Score Methodology) will be used to evaluate continuous variables including QOL score improvements between two groups.

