12.2.3. Propensity Score Methodology

Analyses comparing the treatment groups will be adjusted for the propensity score. The propensity score is the probability that the subject enrolled in the mesh arm rather than the native tissue (control) arm, given the characteristics of the subject and center. The characteristics identified are as follows: age, race, body mass index, smoking, diabetes, post-menopausal, prior prolapse repair, prior hysterectomy, estrogen use, POP-Q C measurement, POP-Q Ba measurement, POP-Q Bp measurement, concomitant repair for stress urinary incontinence, and surgeon case volume. Logistic regression of both treatment arms (i.e., (transvaginal mesh repair vs. native tissue repair) on these characteristics will be used to estimate the propensity score. The subjects will then be partitioned into five strata

corresponding to quintiles of the propensity score. If the balance between treatment arms within the strata is deemed adequate, the treatment difference adjusted for propensity score stratum will be estimated as described in the following.

The propensity adjusted treatment difference will be based on averaging the treatment differences of the propensity score strata. For a binary outcome, the within-stratum treatment difference is $D_j = p_{Tj} - p_{Cj}$, where p_{Tj} and p_{Cj} is the proportion of treatment and control subjects, respectively, in stratum j . The variance of D_j is approximately

$$V_j = \frac{p_{Tj}(1 - p_{Tj})}{n_{Tj}} + \frac{p_{Cj}(1 - p_{Cj})}{n_{Cj}}$$

Denoting the number of subjects in stratum j by $n_j = n_{Tj} + n_{Cj}$, the treatment difference will be estimated by the (weighted) mean of the within-stratum treatment differences

$$D = \sum_j \frac{n_j}{n} D_j$$

where $n = \sum_j n_j$ is the total sample size across all strata and study arms. D is approximately normally distributed with variance

$$V = \sum_j \left(\frac{n_j}{n}\right)^2 V_j$$

from which a confidence interval for the true treatment difference will be constructed. For each continuous outcome, the confidence interval will be constructed similarly, with D and V obtained as above with the treatment difference within each stratum replaced by $D_j = \bar{X}_{Tj} - \bar{X}_{Cj}$, where \bar{X}_{Tj} and \bar{X}_{Cj} , respectively, is the mean of the treatment and control subjects, and

$$V_j = \frac{S_{Tj}^2}{n_{Tj}} + \frac{S_{Cj}^2}{n_{Cj}}$$

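### The between-arm comparisons of quality-of-life, pain and EQ-5D improvement leave out the instrument's own baseline score, which costs precision and leaves any residual baseline gap unadjusted

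*Combined protocol and SAP*

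**What the plan says.** Section 12.1.2.1 states that propensity-adjusted intervals will summarise the "mean score improvement of Quality of Life (PFIQ, PFDI, PISQ, TOMUS pain scale") in the mesh arm against the native tissue arm. Section 12.1.2.3 repeats that these intervals "will be used to evaluate continuous variables including QOL score improvements between two groups". For pain, the same section takes improvement as the quantity analysed, with a paired t-test in each arm and then "with the propensity score adjusted confidence intervals for the pain score differences between groups". The last phrase alone could mean level or change, but Section 12.1.2.1 lists TOMUS under improvement, so change is the natural reading. Section 12.3.6 applies the same intervals to EQ-5D.

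Section 12.2.3 gives the method: "The propensity adjusted treatment difference will be based on averaging the treatment differences of the propensity score strata". For a continuous outcome, each stratum contributes a plain difference of two means, weighted by n_j/n over five quintiles, with no covariate term. The propensity model has 14 characteristics: "age, race, body mass index, smoking, diabetes, post-menopausal, prior prolapse repair, prior hysterectomy, estrogen use, POP-Q C measurement, POP-Q Ba measurement", then "POP-Q Bp measurement, concomitant repair for stress urinary incontinence, and surgeon case volume". None is a baseline PFDI-20, PFIQ-7, PISQ-12, TOMUS or EQ-5D score, although Section 11.4.2 collects all five before surgery.

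Section 12.3.10 also plans ANCOVA for subject-reported outcomes. It is run separately in each treatment group, to look for predictors, and does not name the baseline score.

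**The concern.** The baseline value of a score is usually a strong predictor of the same score later. An analysis that subtracts it instead of adjusting for it carries avoidable noise. That applies in any two-group comparison, whether or not the arms are balanced.

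This study is also non-randomized. Arms follow centre selection, and some controls may come from the registry (Sections 8.1, 8.2, 12.2.2). The propensity strata are the plan's safeguard against imbalance, and Section 12.2.3 proceeds if balance within strata is judged acceptable, without saying that balance in these scores will be checked. If the arms differ in baseline symptoms within strata, nothing in the between-arm estimator adjusts for it.

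At stake are the width, and possibly the location, of the 36-month intervals for patient-reported improvement. The same holds for the 12-month interim report, which may include secondary endpoints (Section 12.3.8).

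**Working it through.** **Inputs from the documents.** Evaluable sample of 165 per arm, 330 in all (Section 8.1); 20% loss (Section 12.1.1.2). Check: 165 / (1 − 0.20) = 206.25, rounded up to 207 per arm, 414 in all, as stated. The documents give no SD, correlation, effect size or power for any of these scores.

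**Assumptions.** Correlation rho between baseline and 36-month score of 0.3 to 0.7; equal SDs at the two times, set to 1; a residual within-stratum baseline gap of 0.2 SD, for illustration only.

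**Precision.** The per-subject variance of a change score is 2(1 − rho). After adjustment for baseline it is 1 − rho². The ratio is (1 + rho)/2. The smallest difference detectable with 80% power at two-sided 0.05 is (1.960 + 0.842) × √(2 × variance / 165).

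| rho | Change variance | Adjusted variance | Ratio | Detectable, change (SD) | Detectable, adjusted (SD) | Adjusted n per arm matching 165 |
|---|---|---|---|---|---|---|
| 0.3 | 1.40 | 0.91 | 0.65 | 0.365 | 0.294 | 108 |
| 0.5 | 1.00 | 0.75 | 0.75 | 0.308 | 0.267 | 124 |
| 0.7 | 0.60 | 0.51 | 0.85 | 0.239 | 0.220 | 141 |

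The last column is 165 × ratio, rounded up. With unequal SDs s0 (baseline) and s1 (follow-up), the variance removed is (s0² + s1² − 2·rho·s0·s1) − s1²(1 − rho²) = (s0 − rho·s1)². This is never negative, so in large samples adjustment does not widen the interval. The size of the gain depends on the SDs.

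**Conditional bias.** Suppose that, with no treatment effect, subjects with the same baseline score have the same expected follow-up in both arms. A baseline gap g then shifts the change-score contrast by (1 − rho) × g in favour of the arm that starts worse. With g = 0.2 SD this is 0.7 × 0.2 = 0.14, 0.5 × 0.2 = 0.10 or 0.3 × 0.2 = 0.06 SD. At 165 per arm, a 95% interval would then exclude zero in about 19%, 15% or 11% of studies with no true effect. For rho = 0.5: SE = √(2 × 1.00 / 165) = 0.110, and the shift is 0.10 / 0.110 = 0.91 SE.

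**Simulation of the Section 12.2.3 estimator** (330 subjects, 1,500 replicates, no true effect, data generated under the equal-follow-up assumption; results at rho 0.3 / 0.5 / 0.7):

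| Situation and analysis | Bias (SD) | Type I error |
|---|---|---|
| Baseline balanced given propensity covariates; planned method | −0.009 / −0.001 / −0.004 | 4.8% / 4.0% / 4.8% |
| Residual gap about 0.28 SD; planned method | −0.20 / −0.14 / −0.08 | 32% / 25% / 14% |
| Same gap; model with arm, stratum and baseline score | −0.005 / −0.001 / 0.004 | 5.1% / 4.5% / 4.9% |
| Same gap; baseline score in the propensity model | −0.03 / −0.02 / −0.01 | 3.5% / 2.9% / 3.6% |

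The planned method is therefore sound when the strata balance the baseline score. Under this assumption it is biased when they do not.

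**The case against.** A reader might infer that the plan compares raw change scores and that the results are biased by regression to the mean. The documents support neither. Improvements are compared within quintiles of a score that includes three POP-Q measurements, prior repair and prior hysterectomy, so baseline symptoms may be partly balanced. No baseline scores are reported, so no residual gap is shown. The entry rule on PFDI-20 question 3 applies to both arms and does not by itself bias the contrast.

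The bias formula also rests on a choice. In a non-randomized comparison, change-score and baseline-adjusted analyses make different untestable assumptions. If the arms would have changed in parallel without a treatment effect, the change score is unbiased. The adjusted estimate is then off by (1 − rho) × g in the opposite direction: the same 0.14, 0.10 or 0.06 SD. This stands, and it is a reason to report both estimates.

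Finally, the endpoint is improvement from baseline, and the intervals are there to summarise it, with no stated null hypothesis, margin or power. That limits the consequence. It does not argue against adjustment: regressing the change score on arm and baseline gives the same arm difference as regressing the follow-up score on them, so the endpoint can stay as it is.

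**Conclusion.** The point holds as a moderate, inexpensive improvement to secondary and additional analyses. The baseline score of the instrument is absent from both the propensity model and the stratum estimator, and the within-arm ANCOVA of Section 12.3.10 does not supply a between-arm estimate.

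The precision loss does not depend on imbalance. Under equal SDs, the planned variance exceeds the adjusted one by 54%, 33% or 18% (1/0.65, 1/0.75 and 1/0.85, each minus 1). Its direction is secure, but its size rests on a correlation and SDs that the documents do not give. Bias is a possibility only: it needs both a within-stratum baseline gap and equal expected follow-up given baseline. No co-primary conclusion is affected.

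**What to change.** In Sections 12.1.2.1, 12.1.2.3 and 12.3.6, for PFDI-20, PFIQ-7, PISQ-12, TOMUS and EQ-5D:

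- Keep the quintiles and n_j/n weights. As the main between-arm estimate, fit ANCOVA within each stratum with the baseline score of the same instrument as covariate, and pool the adjusted differences. A single linear model with arm, stratum and baseline score is an alternative. It weights strata by their information rather than by n_j/n, so the SAP should say which is used.
- Keep the stratified change-score estimate as a sensitivity analysis, and state the assumption behind each.
- Report balance in these baseline scores within strata.
- State that the TOMUS interval is on change from baseline.

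Adding the baseline scores to the propensity model is an acceptable alternative for the bias if done before outcomes are examined, in keeping with Section 12.2.2. It would also change the strata used for the co-primary endpoints and would need a rule for missing baseline scores.

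The cost is SAP wording and a modest amount of extra analysis. No new data are needed, and no subjects are lost by the covariate adjustment, since a change score already requires the baseline value. PGI-I and SSQ-8 have no baseline assessment and are not affected.

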12.1.2.2. Sample Size

The rate of de novo dyspareunia is anticipated to be approximately 9%.²⁴ With type I error of 0.05 and type II error of 0.20 (power 80%), 326 subjects (163 subjects per arm) are needed to detect non-inferiority with a margin of 7.9%.

The rate of AE incidence (pelvic pain, infection, vaginal shortening, atypical vaginal discharge, neuromuscular problems, vaginal scarring, de novo vaginal bleeding, fistula formation and/or de novo voiding dysfunction) is anticipated to be approximately 12%.²² With type I error of 0.05 and type II error of 0.20 (power 80%), 330 subjects (165 subjects per arm) are needed to detect non-inferiority with a margin of 8.9%.

12.1.2.3. Statistical Methods

A comparison of data for all subjects will be included per the following statistical analyses to measure for secondary endpoints:

- Rate of adverse device or procedural-related effects within 6, 12, 18, 24 and 36 months
- Overall rate of adverse device or procedural-related effects within 6, 12, 18, 24, 36 months
- Comparison of adverse device or procedural-related effects between treatment groups
- Rate and severity of mesh exposure and erosion within 6, 12, 18, 24, 36 months
- Assessment of rate of adverse device or procedural-related effects in subjects with reoperation for failed prolapse repair
- Assessment of rates of/times to reoperation
- Comparison of rate of adverse device or procedural-related events in subjects with re-surgery in both treatment groups
- Assessment and comparison between groups of analgesic intake and pain scoring at post-operative 6 weeks, 12, 18, 24, 36 months. Pain score improvement will be analyzed with a paired t-test for each group on all patients and with the propensity score adjusted confidence intervals for the pain score differences between groups. Change in analgesic intake from baseline will be analyzed by McNemar's test for each group on all patients.
- Assessment of severe blood loss during surgical procedure
- Duration of surgery from operative report
- Assessment of re-treatment interventions (i.e. surgery, office-procedure, etc.)
- Assessment of days to discharge and return to normal activity
- Assessment of risk factors, including menopausal status, estrogen use, age smoking, diagnosis of diabetes, body mass index, concomitant procedures, surgeon training and experience

A comparison of data between baseline and 36 months for all subjects will be included per the following statistical analyses to measure for secondary endpoints:

- Quality of Life Assessments (PFIQ, PFDI, PISQ, TOMUS) at 6, 12, 18, 24, 36 months as compared to baseline: paired t-test will be used to compare mean QOL score improvement from baseline to 6, 12, 18, 24 and 36 months for each group.
- Comparison of Quality of Life Assessments improvements between treatment groups
- Assessment of Quality of Life in subjects with re-surgery after re-surgery
- Assessment of subject satisfaction at 6, 12, 18, 24, 36 months (PGI-I for Prolapse)

Propensity score adjusted confidence intervals described in Section 12.2.3 (Propensity Score Methodology) will be used to evaluate continuous variables including QOL score improvements between two groups.

